2.0 TRIAL DESIGN

2.1 Trial Design

This is a double-blinded, parallel, sham-controlled study in PwMS and with significant disability of the upper limb (UL). Participants are exposed to a 6-week run-in period with standard occupational therapy and then randomized to 6 weeks of tSCS or sham combined with ongoing occupational therapy. After completion of the double-blind period, sham-treatment participants will be offered an additional 6 weeks open-label extension (OLE) where they receive active tSCS combined with occupational therapy. Participants in the original active group will be followed with no additional stimulation or occupational therapy to assess the durability of effects. The duration of the run-in, active treatment and extended follow (6 weeks each) are defined based in the previous results from a similar therapy for SCI.

Specific procedures to be performed during the trial, as well as their prescribed times and associated visit windows, are outlined in the Trial Flow Chart - Section 6.0. Details of each procedure are provided in Section 7.0 – Trial Procedures.

2.2 Trial Diagram

The trial design is depicted in [Figure 1](#).

[figure not shown]

Figure 1 Trial Design Diagram

3.0 OBJECTIVE(S) & HYPOTHESIS(ES)

3.1 Co- Primary Objective(s) & Hypothesis(es)

Objectives:

- Objective 1. To assess the safety and tolerability of tSCS in PwMS.
- Objective 2. To assess the preliminary efficacy of tSCS on relevant clinical endpoints for PwMS, including patient-reported outcomes. This will be assessed by the differences in the

nine-hole peg test (9-HPT) affected hand in the tSCS treated vs. sham groups by the end of treatment (V3 vs V5)

Hypothesis:

We hypothesize that cervical tSCS combined with therapy will be tolerable and feasible in PwMS and enhance functional recovery of the upper extremity when compared to occupational therapy alone.

3.2 Key Secondary Objective(s) & Hypothesis(es)**Objectives:**

1. Percentage of responders: 20% difference on the 9HPTd (minimal clinically important difference (MCID)) from baseline to end of the study
2. Change in the 9HPT dominant and non-dominant hand from baseline to end of the study
3. Change in the Action Research Arm Test (ARAT) from baseline to end of the study
4. Change in the modified Ashworth Scale (mAS) for spasticity assessment from baseline to end of the study
5. Hand strength measured by Grip and Pinch force dynameters from baseline to end of the study
6. Change in the NeuroQOL Upper Extremity function from baseline to end of the study
7. Change in the Modified Fatigue Impact Scale (MFIS) from baseline to end of the study
8. Change in Global Impression of change (GIC) from baseline to end of the study

Hypothesis: Our hypothesis is that tSCS treatment of the cervical cord combined with occupational therapy is safe and efficacious for treating people with MS with moderate to severe upper limb (hands) disability. Recent multi-site clinical trials in patients with spinal cord injury (SCI) have shown excellent safety and efficacy of tSCS associated with occupational therapy to improve UL functioning (NCT04697472). Therefore, this relevant evidence support moving this therapy directly to people with MS (PwMS) with moderate to severe UL disability.

3.3. Exploratory endpoints

None

Hypothesis: NA

3.4. Safety endpoints

Safety and Tolerability Objectives:

1. Adverse Events (AEs) and Serious Adverse Events (SAEs):

All adverse events, regardless of severity or relatedness to the intervention, will be collected and documented throughout the study period. This includes both serious and non-serious adverse events. Serious adverse events will be defined according to ICH-GCP guidelines as any event that results in death, is life-threatening, requires inpatient hospitalization or prolongation of existing hospitalization, results in persistent or significant disability/incapacity, or a congenital anomaly/birth defect.

2. Discontinuations and Reasons for Discontinuation:

Participant retention will be assessed by monitoring the number of participants who discontinue the study prior to its completion. The reasons for discontinuation (e.g., adverse events, lack of efficacy, personal decision, protocol deviations) will be recorded systematically.

3. Retention Rate:

The retention rate will be defined as the percentage of participants who complete the study intervention and all study visits relative to the total number of participants initially randomized.

4. Attendance Rate:

The percentage of scheduled intervention sessions that each participant attends will be recorded to assess adherence and tolerability.

Hypothesis: We hypothesize that tSCS will be safe and well tolerated in PwMS, with a low incidence of serious adverse events and a high retention rate.

4. BACKGROUND & RATIONALE

4.1 Background

4.1.1 Therapeutic Background

Multiple sclerosis (MS) is a relapsing and/or progressive disease characterized by lesions comprised of demyelination and axonal loss throughout the brain and/or spinal cord¹. Current disease-modifying therapies aim to prevent the development of new lesions; unfortunately, there are no current FDA-approved therapies to promote Central Nervous System (CNS) repair mechanisms. Thus, strategies to promote functional recovery from lesion-related deficits in adults with multiple sclerosis remain an unmet need.

Electrical spinal cord stimulation is a neuromodulation technique that has been used to amplify sensorimotor recovery after a wide variety of CNS disorders, including MS, traumatic spinal cord injury (SCI), cerebral palsy, dystonia, stroke, and traumatic brain injury². Historically, implantable epidural electrical stimulators were used, but despite initial promising results, the requirement of surgically implantable hardware and lack of understanding of the mechanism of action limited its use³. Most recently, however, we

[figure not shown]

Figure 2: Transcutaneous electrical spinal stimulation is applied to the skin surface over the cervical spinal cord. In our preliminary studies of a person with MS, and our extensive studies of people with chronic spinal cord injury, this transcutaneous spinal stimulation substantially improves hand strength and function.

have helped to pioneer new methods of non-invasive transcutaneous spinal cord stimulation^{4, 5} (tSCS; Figure 2).

[figure not shown]

Figure 3: Transcutaneous spinal stimulation applied via electrodes placed above and below a cervical spinal injury. A 10 kHz carrier frequency fills the 1ms stimulus pulses delivered at 30 Hz, allowing 5-fold more current to be delivered to the skin over the spinal cord and improve hand function.

We are using a 10 kHz overlapping frequency to apply skin-surface stimulation (Figure 3). This high-frequency waveform allows the application of 5-fold greater stimulation intensities through the skin⁶⁻⁸, which effectively reaches the spinal cord without causing discomfort^{4-7, 9}. Thus, tSCS now permits administration of effective and well-tolerated, high stimulation intensities via removable electrodes placed on the skin over the vertebrae. While our tSCS protocols are less spatially specific than implanted epidural stimulation, both activate the dorsal sensory roots as they enter the spinal cord^{3, 10-12}. Activation of sensory afferent fibers provides direct excitation of motor neurons via mono-and poly-synaptic reflexes to improve strength and function^{4-6, 9}. Stimulation likely also activates ascending sensory and other interneuron structures within the spinal cord to improve sensation and reduce spasticity without the need for surgical implantation^{5, 6}.

We have demonstrated that our method of tSCS is well-tolerated and promotes significant and meaningful recovery of upper extremity function after chronic traumatic spinal cord injury^{4, 6, 13-15}. For example, a prospective, open-label cross-over studies showed that non-invasive tSCS combined with functional task training improved upper extremity function in adults with SCI compared to functional task training alone, even after motor complete injury, and when administered up to 12 years after initial injury (Figure 4)⁴.

[figure not shown]

Figure 4: Stimulation improved hand and arm function, which was sustained for 3-6 months in participants with cervical spinal cord injury. All six participants improved hand function during transcutaneous stimulation paired with training. Stimulation combined with training led to greater improvements than training alone in bilateral (A) pinch force, (B) Graded Redefined Assessment of Strength, Sensation and Prehension (GRASSP test), and (C) GRASSP quantitative prehension. Improvements that occurred during stimulation paired with training were maintained for at least 3 to 6 months of follow-up. *: $p < 0.05$; NS: $p > 0.05$.

Strikingly, these gains were maintained for all 6 participants at least 3-6 months beyond stimulation, as long as could be measured. Also notable was the finding that benefits from this study extended beyond hand function, as some participants noted improvements in bladder function and reduction in spasticity. Improvements in psychological well-being, and self-care scores were also captured.

[figure not shown]

Figure 4. tSCS improves strength and function in 60 people with SCI. Our pivotal of tSCS began with 8 weeks of therapy alone (grey data points and lines), followed by 8 weeks of transcutaneous spinal stimulation combined with therapy (red data points and lines). While participants either reached a plateau or showed no improvement with therapy alone, subsequent tSCS led to significant improvements in strength and sensation, with 90% of participants improving in strength or function outcomes. Strength measures included INSCSCI

Upper Extremity Motor Score (UEMS), hand grasp force, and finger-tip pinch force. Sensory outcomes were ISNCSCI Sensory Score, Upper Extremity Sensory Score (UESS) and monofilament finger-tip sensation in the GRASSP test.

We then led a pivotal, multi-site trial of 60 participants with traumatic SCI and demonstrated the safety and efficacy of tSCS for arm and hand function in chronic tetraplegia⁵ (Figure 4). Following 8 weeks of tSCS combined with hand therapy, 90% of participants improved in either strength or function outcomes. Seventy-two percent of participants improved in both strength and function (the primary endpoint). Sensation also improved following tSCS by more than 9 points on the gold-standard clinical ISNCSCI total sensory score, compared to an equal number of sessions of therapy alone. These results are currently under review by the FDA following a do-novo submission by ONWARD Medical, for potential device approval in early 2024.

We are beginning to test tSCS for people with multiple sclerosis (PwMS) and observing impressive results in our first participant (see preliminary data below). Although the lesions in MS are distributed throughout the brain and spinal cord, there is strong evidence to suggest that spinal stimulation, and tSCS in particular, will be similarly effective for PwMS as those with SCI^{4-7, 9, 16}, stroke¹⁷, and children with cerebral palsy¹⁸⁻²⁰, based on the mechanisms of action of tSCS.

Evidence is accumulating that the combination of tSCS and intensive functional task training (therapy) promotes recovery via the following mechanisms (outlined in Figure 5). tSCS directly activates sensory afferent pathways via the dorsal or posterior spinal roots^{3, 10-12}. Sensory afferent activation then provides trans-synaptic, sub-threshold excitatory input to the lower motor neurons within the spinal cord²¹. This sub-threshold input is believed to raise the motor neuron's baseline level of excitability, which allows spinal cord motor neuron pools to be activated by the remaining, but weak, descending motor pathways from the brain²². Thus, by raising the lower motor neuron's level of excitability to a sufficient sub-threshold level, descending volitional control of movement can be restored²³. Continued active participation in rehabilitation training can then promote further reorganization of the spinal networks and strengthen the remaining intact but weak synaptic connections²⁴⁻²⁶.

[figure not shown]

Figure 5. A schematic of the mechanism by which spinal cord stimulation enables voluntary movement after damage to descending motor tracts from SCI or MS. **1.** In the intact nervous system, a voluntary effort can readily elevate the level of excitability of the lower motor neuron to exceed the motor threshold and activate a muscle contraction; **2.** Following nervous system injury or demyelination, descending motor tracts from the brain are less effective in allowing an individual to initiate movement. There is some electrical activity from remaining intact fibers, but the level of excitability is insufficient to reach motor threshold. Hence, no movement occurs; **3.** In the case of nervous system injury or demyelination + electrical stimulation, spinal stimulation raises the level of excitability to a sub-threshold level; this can enable the weak but remaining descending input from the brain to exceed the motor threshold. Voluntary movement is restored and enables participation in therapy which leads to further neuroplasticity.

The mechanisms of tSCS suggest it may be very effective for persons with multiple sclerosis. Multiple Sclerosis (MS) is a chronic, inflammatory demyelinating condition characterized by multiple lesions disseminated throughout the brain and spinal cord. Thus, weakness may occur due to inadequate motor output from the brain, similar to stroke and cerebral palsy. Weakness in MS may also result from axon conduction failure in signals passing through the spinal cord, as in spinal cord injury.

There are notable similarities between MS and SCI as well as dissimilarities. Chronic spinal cord lesions in each condition are characterized by demyelination, axonal loss, and chronically activated microglia^{27, 28}. The list of resulting symptoms and functional impairments are remarkably similar: motor weakness, sensory impairment, spasticity, neuropathic pain, and neurogenic bowel/bladder are highly prevalent in both conditions^{29, 30}. Therefore, similar to SCI, we hypothesize that spinal stimulation in people with MS has the potential to bring lower motor neurons closer to the threshold, allowing weak but descending input from the brain to initiate movement (Figure 5).

Although most of the research on SCS has been conducted in humans, the beneficial effect of tSCS in animal models of SCI and MS has also been demonstrated. SCS has shown the ability to restore the functioning of spinal cord circuits that were disconnected from central control with functional (locomotor and pain reduction) improvements in the animals³¹⁻³⁴. In experimental autoimmune encephalomyelitis, SCS reduces CNS inflammation³⁵ and promotes the release of neuroprotective genes such as BDNF³⁶.

Although transcutaneous spinal cord stimulation has not been well-studied in PwMS, electric stimulation has been applied peripherally to the nerve supply of weak muscles (e.g., foot extensors) to restore function and prevent muscle atrophy in PwMS³⁷⁻³⁹. Existing data

on epidural spinal cord stimulation in MS also shows promise: a 2021 systematic review concluded that spinal cord stimulation was likely efficacious for MS-related motor impairment, neuropathic pain, and neurogenic bladder, although all available studies used only surgically implanted devices and were only retrospective in nature⁴⁰.

Less is known about the efficacy of transcutaneous SCS in MS, which highlights the novelty of our proposal. One prior study demonstrated that the application of single-session transcutaneous lumbar spinal cord stimulation without therapy is feasible in MS and demonstrated short-term improvements in mobility, postural control and spasticity⁴¹. An important proof-of-concept study in MS, functional gains from this single session of transcutaneous lumbar spinal cord stimulation lasted 2 hours post-intervention.

To our knowledge, the proposed study will be the first to investigate the ability of repeated transcutaneous cervical spinal cord stimulation combined with occupational therapy on longer-term recovery of upper extremity function, which is identified as a high priority by the MS community^{42, 43}.

An alternative to electrical spinal cord stimulation is transcranial magnetic stimulation (TMS), which has shown some promise in PwMS⁴⁴. Here, however, we propose to use tSCS instead of TMS based on the wider efficacy demonstrated in SCI by tSCS, the latest improvement of the tSCS technology to non-invasively activate the spinal cord without pain or discomfort. We believe that the direct effects of spinal cord electric stimulation on sensory axons which in turn enable movement is the ideal treatment for PwMS, given their partial preservation of cortical and spinal cord circuits. Our encouraging preliminary data, combined with the demonstrated safety and efficacy of tSCS in SCI, compels us to test non-invasive spinal stimulation as a treatment to improve hand function for PwMS.

This application aims to conduct a pilot clinical trial to demonstrate the safety and preliminary efficacy of tSCS and to inform the design of pivotal trials aimed at obtaining regulatory approval for the indication of treating people with MS with moderate to severe upper limb disability. We model this approach after our recent proof-of-concept^{4, 6} and then multi-site clinical trial⁵ in people with SCI where we have demonstrated the safety and efficacy of tSCS combined with intensive occupational therapy to improve upper extremity functioning. The results of this pivotal trial, combined with our strong preliminary data, supports moving this therapy directly to PwMS with moderate to severe upper limb disability.

Preliminary Results

4.2 Rationale

4.2.1 Rationale for the Trial and Selected Subject Population

Current disease-modifying therapies aim to prevent the development of new lesions; unfortunately, there are no current FDA-approved therapies to promote Central Nervous System (CNS) repair mechanisms. Thus, strategies to promote functional recovery from lesion-related deficits in adults with multiple sclerosis remain an unmet need. This proposal seeks to remedy this significant gap in MS care.

4.2.2 Rationale for Stimulation Protocols Selection/Regimen

The tSCS non-invasive spinal stimulation utilizes two modulated frequencies: (1) base frequency and (2) overlapping frequency. The base frequency is 30 Hz, whereby 1ms pulses are delivered 30 times per second (Figure 12 right). Within each pulse, an overlapping frequency of 10kHz is deployed to permit about 5-fold more current to be delivered for the same level of cutaneous sensation under the electrodes. This 10 kHz overlapping frequency is adapted from kilohertz-frequency muscle stimulation, permitting high-amplitude stimulation on the skin surface without discomfort. Thus, stimulation applied on the surface of the skin can reach the spinal cord dorsal roots to activate spinal networks. The rationale for the 10 kHz overlapping frequency is that high-frequency waveforms can selectively block unmyelinated C-fibers in the skin^{50, 51}, and stimulation may penetrate more deeply due to the lowering of the tissue impedance^{4, 6, 52}. We have observed substantial improvements in hand and arm function without inducing discomfort under the electrodes in our studies of more than 70 people with spinal cord injury⁴⁻⁶.

4.2.2.1 Rationale for the Use of Sham

In order to assess the efficacy of the therapy in clinical outcomes, comparison between active and sham treatment is required. Using sham or placebo for 6 weeks is accepted for patients with MS. In order to encourage participation and fulfill patients' expectations, sham treated patients will be offered an additional 6 weeks open-label extension (OLE) where they receive active tSCS combined with occupational therapy.

4.2.2.2 Rationale for Healthy Control

No healthy control group is required.

4.2.2.2 Starting Stimulation Protocols for This Trial

The base frequency is 30 Hz, whereby 1ms pulses are delivered 30 times per second (Figure 12 right). Within each pulse, an overlapping frequency of 10kHz is deployed to permit about 5-fold more current to be delivered for the same level of cutaneous sensation under the electrodes.

4.2.3 Rationale for Endpoints

4.2.3.1 Efficacy Endpoints

Primary endpoints: the 9HPT is the accepted outcome for UL assessment in MS.

Secondary endpoints: In addition to the 9HPT, the ARAT, MAS, NeuroQOL, MFIS, and GIC are standard scales used in patients with MS

4.2.3.2 Safety Endpoints

The safety and tolerability of tSCS will be assessed throughout the study via Adverse Event reporting, and vital signs will be assessed at every trial visit.

4.3 Benefit/Risk

Participants in this study are patients with MS with severe disability involving UL (and most likely with severe lower limb disability, being restricted to a wheelchair) or having significant ambulation limitations). tSCS is not invasive, is well tolerated and is a minimal-risk device. As a result, the risk/benefit should be highly beneficial for the participants.

5.0 METHODOLOGY

5.1 Entry Criteria

5.1.1 Diagnosis/Condition for Entry into the Trial

Patients with MS (McDonald criteria 2017) with moderate to severe upper-limb disability defined as 9HPT in the dominant hand/functional hand > 33.3 sec (range: 33.3-240 sec)

5.1.2 Subject Inclusion Criteria

In order to be eligible for participation in this trial, the subject must:

1. Be between 21 to 65 years of age (inclusive) on the day of signing informed consent.
2. Have MS (McDonald criteria 2017) with moderate to severe upper-limb disability defined as 9HPT in the dominant hand/functional hand > 33.3 sec (range: 33.3-240 sec)
3. Any type of disease modifying therapy is allowed and should be stable in the last 3 months.
4. Not having received corticosteroids previous month.
5. Each subject must sign the informed consent form, in accordance with local requirements, after the scope and nature of the investigation have been explained to the subject, and before Screening assessments.
6. Based on the investigator's judgment, the subject should:
 - a. Be able to speak, read, and understand the language of the trial staff and the informed consent form;
 - b. Possess the ability to respond verbally to questions, follow instructions, and complete study assessments.
 - c. Be able to adhere to the stimulation protocol and visit schedules.
7. Women of child-bearing potential* must have a negative urine pregnancy test before the inclusion in the study and agree to use highly effective contraceptive methods during the study. Highly effective contraceptive methods will include intrauterine device, implant, patch or pill, bilateral tubal occlusion, vasectomized partner and sexual abstinence.

* A woman will be considered of childbearing potential, following menarche and until becoming post-menopausal unless permanently sterile. Permanent sterilization methods include hysterectomy, bilateral salpingectomy and bilateral oophorectomy. A postmenopausal state is defined as 0 menses for 12 months without an alternative medical cause. A high follicle stimulating hormone level in the postmenopausal range may be used to confirm a post- menopausal state in women not using hormonal

contraception or hormonal replacement therapy. However, in the absence of 12 months of amenorrhea, a single follicle stimulating hormone measurement is insufficient.

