7.2.2 Reporting of Pregnancy and Lactation

Female participants may screen for this study if:

- They are surgically sterile [have had a hysterectomy (uterus removed), bilateral oophorectomy (ovaries removed), or tubal ligation at least 6 months prior]
- They are of post-menopausal age and have not had a menstrual period for 12 months
- They have a vasectomized partner (performed at least 6 months prior) who has been documented to no longer produce sperm
- They are using a highly effective method of contraception to avoid pregnancy throughout the study and for 30 days after you complete this study.

Examples of acceptable forms of highly effective contraception include:

1. Established use of oral, injected or implanted hormonal methods of contraception plus use of a condom for your male partner.
2. Placement of an intrauterine device (IUD) or intrauterine system (IUS) plus use of a condom for your male partner.
3. True abstinence: When this is in line with your preferred and usual lifestyle

NOTE: Periodic abstinence (e.g., calendar, ovulation, symptothermal, post ovulation methods), condoms alone or double barrier are not acceptable methods of contraception.

Male participants must ensure a condom is used for all sexual intercourse as well as following the acceptable methods of contraception listed above for your female partner and ensuring that they are used for the entire duration of the study, and for at least 90 days after you complete this study.

Although pregnancy and lactation are not considered adverse events, it is the responsibility of investigators or their designees to report any pregnancy or lactation in a subject (spontaneously reported to them) that occurs during the trial.

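### Inclusion criterion 7 (section 5.1.2) and section 7.2.2 state different contraception and sterility conditions, and the two passages must be reconciled

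*Protocol*

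**What the plan says.** **Protocol section 5.1.2, inclusion criterion 7.** A woman of child-bearing potential needs a negative urine pregnancy test and must "agree to use highly effective contraceptive methods during the study". The accepted methods are: "Highly effective contraceptive methods will include intrauterine device, implant, patch or pill, bilateral tubal occlusion, vasectomized partner and sexual abstinence". The footnote then defines who is no longer of child-bearing potential: "Permanent sterilization methods include hysterectomy, bilateral salpingectomy and bilateral oophorectomy". Tubal occlusion appears among the contraceptive methods, not among the sterilisation methods.

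**Protocol section 7.2.2.** The heading concerns the reporting of pregnancy and lactation, but the text opens with "Female participants may screen for this study if" and gives four routes. The surgical route reads "They are surgically sterile [have had a hysterectomy (uterus removed), bilateral oophorectomy (ovaries removed), or tubal ligation at least 6 months prior". The partner route reads "They have a vasectomized partner (performed at least 6 months prior) who has been documented to no longer produce sperm". The other two are menopause and use of a highly effective method throughout the study and for 30 days afterwards. A list of examples follows, including "Established use of oral, injected or implanted hormonal methods of contraception plus use of a condom for your male partner" and an IUD or IUS, also with a condom. Men are then addressed: "Male participants must ensure a condom is used for all sexual intercourse", together with contraception for the female partner, for the study and at least 90 days after it.

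Neither section 5.1.2 nor section 5.1.3 contains a contraception criterion for men.

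**The concern.** Eligibility should have one source. Here a section on reporting carries its own screening language for women, and its conditions do not match the inclusion criterion. Patients are recruited at three hospitals in Barcelona and one centre in the Netherlands. A centre working from section 5 and a centre (or monitor) working from section 7.2.2 could classify the same woman differently, and one could record a deviation where the other sees none.

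The second consequence concerns what participants are told. The two sections give different end dates for contraception, and men are given a post-study obligation that no eligibility check raises.

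**Working it through.** No figure in the plan bears on this point, so there is nothing to recalculate. The check is an item-by-item comparison of section 5.1.2 (criterion 7) with section 7.2.2, and a search of 5.1.3 for any criterion on men. The four routes in 7.2.2 are read as alternatives, since no woman could be expected to meet all of them.

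| Item | Section 5.1.2 | Section 7.2.2 | Kind of difference |
|---|---|---|---|
| Partner vasectomised | accepted, no conditions | at least 6 months ago, absence of sperm documented | eligibility |
| Tubal occlusion or ligation, recent | accepted as contraception, no time limit | not sterility until 6 months have passed | eligibility |
| Tubal occlusion or ligation, 6 months or more | contraception in a woman still of child-bearing potential, so pregnancy test needed | surgically sterile | classification |
| Bilateral salpingectomy alone | permanent sterility, no contraception needed | not listed | eligibility |
| Hormonal method or IUD | stands alone | examples shown with a condom | wording, see objection |
| Patch | named | not named among the examples | wording |
| Duration, women | during the study | study plus 30 days | obligation |
| Men | no criterion (also none in 5.1.3) | condom and partner contraception, study plus at least 90 days | obligation |

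Three situations separate the sections on entry:

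1. **Partner's vasectomy under 6 months old, or without documentation.** It satisfies criterion 7 and fails the specific vasectomy condition in 7.2.2.
2. **Tubal procedure under 6 months old.** It satisfies criterion 7 as a method and fails the sterility condition in 7.2.2.
3. **Bilateral salpingectomy with no other measure.** Criterion 7 asks for nothing further. No sterility item in 7.2.2 covers it, so the woman would need another route.

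A fourth situation, the older tubal procedure, leads to entry under both sections but with a different status. Criterion 7 asks for a pregnancy test, whereas 7.2.2 groups her with women who have had a hysterectomy.

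The definitions of menopause agree on 12 months without menses.

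The duration and male items exclude nobody at screening. They are differences in what participants must do, and for how long.

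**The case against.** The strongest reply is that most of the apparent conflict is loose drafting. Section 7.2.2 addresses the participant in the second person and reads like consent text carried into the protocol. Section 4.3 describes the device as minimal-risk, and section 9.0 says that no drug is tested. Much of this reply stands, and it limits the point in five ways.

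- **Pill, implant or IUD without a condom.** A reader might infer that 7.2.2 refuses these women. The text does not support that. The condom pairings are introduced as examples, the methods expressly rejected are periodic abstinence, condoms alone and double barrier, and the condition itself is only use of a highly effective method.
- **Duration and men.** These are conduct obligations. Following the longer period satisfies both sections, and the screening sentence covers women only. They are inconsistencies in what participants are told, not entry conflicts.
- **Withdrawal of enrolled participants.** A reader might infer that section 7.1.1.2 would remove patients who fail 7.2.2. That section refers to the inclusion and exclusion criteria, which are 5.1.2 and 5.1.3. It does not clearly reach 7.2.2.
- **Protection during stimulation.** A reader might infer that one section leaves it uncovered. Both require highly effective contraception throughout the study, and 5.1.3 excludes pregnant women.
- **Reading the 5.1.2 list into 7.2.2.** Because the examples are open, a site could admit a recent tubal occlusion or vasectomy through the general route of a highly effective method. That removes the conflict only by leaving the 6-month and documentation conditions with no effect. It does not help with salpingectomy, which 5.1.2 classes as sterility and not as a contraceptive method.

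What survives is the disagreement on vasectomy, tubal procedures and salpingectomy, together with the differing obligations. The informal origin of the text may explain these, but sites still have two written rules.

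**Conclusion.** The two sections contradict each other on the conditions for a vasectomised partner, on the status and timing of tubal occlusion or ligation, and on whether bilateral salpingectomy counts as sterility. They also differ on how long contraception lasts, on condom use in the listed methods, and on whether men carry any obligation. Sites can reach different eligibility decisions in those narrow situations and can tell participants different things.

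The point is minor. The number of participants affected cannot be derived, because the protocol gives no expected sex split, no proportion of women of child-bearing potential and no distribution of contraceptive methods. Any count would be a product of assumed proportions. Sample size, power, the primary endpoint and its analysis are unaffected.

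The conclusion assumes that the opening sentence of 7.2.2 is meant as a screening condition, as it is worded. If the sponsor intended only reporting, the same text still needs to go.

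**What to change.** Reconcile the two passages into one set of conditions in section 5.1.2, covering:

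- one list of accepted methods, stating whether any must be combined with a condom;
- one definition of sterility that places tubal occlusion or ligation and bilateral salpingectomy explicitly and says who needs a pregnancy test;
- any time or documentation condition for a partner's vasectomy or a tubal procedure, or a statement that there is none;
- one end date for contraception;
- a criterion or obligation for men, if one is intended.

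Limit section 7.2.2 to the reporting of pregnancy and lactation, with a cross-reference to 5.1.2. Which conditions apply is for the sponsor to decide. This review proposes none.

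The cost is a wording amendment and a check that the consent text matches. The reconciliation itself requires no added procedure and no change to the sample size or analysis.
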